3.5 CRITERIA FOR REMOVAL FROM PROTOCOL THERAPY AND OFF STUDY CRITERIA

3.5.1 Criteria for removal from protocol therapy

The criteria that take the subject off active protocol therapy include:

- Progressive disease on each study arm
- Participant requests to be withdrawn from active therapy
- Unacceptable Toxicity as defined in Section **3.3**
- Investigator discretion
- Positive pregnancy test

In all cases, a safety follow up visit will be conducted within approximately 30 days of the last dose of study drug therapy.

3.5.2 Off-Study Criteria

The criteria that take the subject off study include:

- Participant requests to be withdrawn from study*
- Patient lost to follow up
- Investigator discretion
- Screen failure
- Death
- PI decision to close the study

* If patient is still on active therapy at the time of request, patients will be encouraged to undergo a follow up safety visit approximately 30 days from the last dose of study drug prior to being removed from the study.

3.5.3 Off Protocol Therapy and Off Study Procedure

Authorized staff must notify Central Registration Office (CRO) when a subject is taken off protocol therapy and when a subject is taken off-study. A Participant Status Updates Form from the website (<http://home.ccr.cancer.gov/intra/eligibility/welcome.htm>) main page must be completed and sent via encrypted email to: NCI Central Registration Office [contact].

4 CONCOMITANT MEDICATIONS/MEASURES

4.1 SUPPORTIVE CARE

- Long-acting octreotide (Sandostatin® LAR Depot) is a somatostatin analogue which has been used in combination with everolimus or sunitinib for symptoms control[49, 57]. Common side effects of long-acting octreotide include gallstones (24%), hyperglycemia (27%) and hypoglycemia (4%). Octreotide will be only administered to patients with carcinoid syndrome for symptom control and patients already on it will be continued on the medication.
- Long-acting octreotide will be administered at a dose of 30 mg intramuscularly every 28 days for control of carcinoid symptoms or at the dose the patient is already on at enrollment.
- Standard medical therapy will be utilized in the management of everolimus and sunitinib toxicity. The sections provide recommendations for management of specific toxicities.

4.1.1 Management of Sunitinib-Induced Hypertension

Table 10 Oral Antihypertensive Medications

Agents in bold characters are suggested as optimal choices to avoid or minimize potential drug-interactions with sunitinib through CYP450.

Agent class	Agent	Initial dose	Intermediate dose	Maximum dose	Hepatic metabolism
Dihydro-pyridine Calcium-Channel Blockers (DHP CCB)	nifedipine XL	30 mg daily	60 mg daily	90 mg daily	CYP 3A4 substrate
	amlodipine	2.5 mg daily	5 mg daily	10 mg daily	CYP 3A4 substrate
	felodipine	2.5 mg daily	5 mg daily	10 mg daily	CYP 3A4 substrate and inhibitor
Selective β Blockers (BB)	metoprolol	25 mg twice daily	50 mg twice daily	100 mg twice daily	CYP 2D6 substrate
	atenolol	25 mg daily	50 mg daily	100 mg daily	No

Agent class	Agent	Initial dose	Intermediate dose	Maximum dose	Hepatic metabolism
	acebutolol	100 mg twice daily	200-300 mg twice daily	400 mg twice daily	Yes (CYP450 unknown)
	bisoprolol	2.5 mg daily	5-10 mg daily	20 mg daily	Yes (CYP450 unknown)
Angiotensin Converting Enzyme Inhibitors (ACEIs)	captopril	12.5 mg 3x daily	25 mg 3x daily	50 mg 3x daily	CYP 2D6 substrate
	enalapril	5 mg daily	10-20 mg daily	40 mg daily	CYP 3A4 substrate
	ramipril	2.5 mg daily	5 mg daily	10 mg daily	Yes (CYP450 unknown)
	lisinopril	5 mg daily	10-20 mg daily	40 mg daily	No
	fosinopril	10 mg daily	20 mg daily	40 mg daily	Yes (CYP450 unknown)
	Rarely used: perindopril	4 mg daily	none	8 mg daily	Yes, but not CYP450
	Rarely used: quinapril	10 mg daily	20 mg daily	40 mg daily	No
Angiotensin II Receptor Blockers (ARBs)	losartan	25 mg daily	50 mg daily	100 mg daily	CYP 3A4 substrate
	candesartan	4 mg daily	8-16 mg daily	32 mg daily	CYP 2C9 substrate
	irbesartan	75 mg daily	150 mg daily	300 mg daily	CYP 2C9 substrate
	telmisartan	40 mg daily	none	80 mg daily	Yes, but not CYP450
	valsartan	80 mg daily	none	160 mg daily	Yes, but not CYP450
α and β Blocker	labetalol	100 mg twice daily	200 mg twice daily	400 mg twice daily	CYP 2D6 substrate and inhibitor

4.1.2 Management of specific everolimus toxicities

Overall, safety data available from completed, controlled and uncontrolled studies indicate that everolimus is generally well tolerated at weekly or daily dose schedules. The safety profile is characterized by manageable adverse events (AEs). These AEs are generally reversible and non-cumulative.

Adverse events most frequently observed with everolimus are stomatitis, rash, diarrhea, fatigue, infections, asthenia, nausea, peripheral edema, decreased appetite, headache, dysgeusia, epistaxis, mucosal inflammation, pneumonitis, weight decreased, vomiting, pruritus, cough, dyspnea, dry skin, nail disorder, and pyrexia. . Overall, the most frequently observed laboratory abnormalities include decreased hematology parameters including hemoglobin, lymphocytes, platelets, and neutrophils (or collectively as pancytopenia); increased clinical chemistry parameters including cholesterol, triglycerides, glucose, aspartate transaminases, creatinine, alanine transaminases, and bilirubin; and decreased clinical chemistry parameters including phosphate and potassium. The majority of these AEs have been of mild to moderate severity (NCI CTC grade 1-2).

4.1.2.1 Management of infections

Everolimus has immunosuppressive properties and may predispose patients to bacterial, fungal, viral or protozoal infections, including infections with opportunistic pathogens. Localized and systemic infections, including pneumonia, other bacterial infections, invasive fungal infections, such as aspergillosis or candidiasis and viral infections including reactivation of hepatitis B virus, have been described in patients taking everolimus. Some of these infections have been severe (e.g. leading to sepsis, respiratory or hepatic failure) and occasionally have had a fatal outcome.

Physicians and patients should be aware of the increased risk of infection with everolimus. Treat pre-existing infections prior to starting treatment with everolimus. While taking everolimus, be vigilant for symptoms and signs of infection; if a diagnosis of infection is made, institute appropriate treatment promptly and consider interruption or discontinuation of everolimus.

If a diagnosis of invasive systemic fungal infection is made, discontinue everolimus and treat with appropriate antifungal therapy.

Cases of pneumocystis jirovecii pneumonia (PJP), some with a fatal outcome, have been reported in patients who received everolimus. PJP may be associated with concomitant use of corticosteroids or other immunosuppressive agents. Prophylaxis for PJP should be considered when concomitant use of corticosteroids or other immunosuppressive agents are required.

4.1.2.2 Management of skin toxicity

For patients with grade 1 toxicity, no specific supportive care is usually needed or indicated. Rash must be reported as an AE. Patients with grade 2 or higher toxicity may be treated with the following suggested supportive measures at the discretion of the investigator: oral minocycline, topical tetracycline, topical clindamycin, topical silver sulfadiazine, diphenhydramine, oral prednisolone (short course), topical corticosteroids, or pimecrolimus.

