1.2.3.3 Safety Profile

Sunitinib is reasonably well tolerated, with asthenia, hypertension, dermatitis, and mild myelosuppression as the most common AEs.[93] Additionally, the inhibition of TKRs by agents such as sunitinib can result in cutaneous AEs such as acral erythema, subungual splinter hemorrhages, modification of hair and skin pigmentation, mucositis, and (occasionally) periocular edema[94, 95]. Hand-foot skin reaction, a group of signs and symptoms that can affect, usually bilaterally, the hands and/or feet of patients, has occurred in patients receiving sunitinib. A recent analysis of dermatological AEs in patients receiving sunitinib therapy has

reported that all-grade hand-foot skin reactions occurred in 19% of patients (5% grades 3-4), skin discoloration in 28% (no grades 3-4), dry skin in 16% (1% grades 3-4), skin rash in 13% (1% grades 3-4), dermatitis in 8% (2% grades 3-4), hair color changes in 10% (no grades 3-4), alopecia in 6% (no grades 3-4), and phototoxicity in <0.1% (no grades 3-4)[96].

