4.1.2.6 Management of stomatitis / oral mucositis / mouth ulcers

Adverse Drug Reaction	Severity	Everolimus Dose Adjustment and Management Recommendations
Stomatitis	Grade 1 (Minimal symptoms, normal diet)	No dose adjustment required. Manage with non-alcoholic or salt water (0.9%) mouth wash several times a day.
	Grade 2 (Symptomatic but can eat and swallow modified diet)	Temporary dose interruption until recovery to grade ≤ 1 . Re-initiate everolimus at the same dose. If stomatitis recurs at grade 2, interrupt dose until recovery to grade ≤ 1 . Re-initiate everolimus at one dose level lower. Manage with topical analgesic mouth treatments (e.g. benzocaine, butyl aminobenzoate, tetracaine hydrochloride, menthol or phenol) with or without topical corticosteroids (i.e. triamcinolone oral paste)*.
	Grade 3 (Symptomatic and unable to adequately eat or hydrate orally)	Temporary dose interruption until recovery to grade ≤ 1 . Re-initiate everolimus at one dose level lower. Manage with topical analgesic mouth treatments (i.e. benzocaine, butyl aminobenzoate, tetracaine hydrochloride, menthol or phenol) with or without topical corticosteroids (i.e. triamcinolone oral paste)*
	Grade 4 (Symptoms associated with life-threatening consequences)	Discontinue everolimus and treat with appropriate medical therapy.

* using agents containing alcohol, hydrogen peroxide, iodine, and thyme derivatives in management of stomatitis as they may worsen mouth ulcers.

Patients with a clinical history of stomatitis/mucositis/mouth ulcers and those with gastrointestinal morbidity associated with mouth/dental infections, irritation of esophageal mucosa e.g. gastroesophageal reflux disease (GERD) and pre-existing stomatitis/mucositis must be monitored even more closely. Patients should be instructed to report the first onset of buccal mucosa irritation/reddening to their study physician immediately.

Stomatitis/oral mucositis/mouth ulcers due to everolimus should be treated using local supportive care. Please note that investigators in earlier trials have described the oral toxicities associated with everolimus as mouth ulcers, rather than mucositis or stomatitis. If your examination reveals mouth ulcers rather than a more general inflammation of the mouth, please classify the adverse event as such. The suggested paradigm for treatment of stomatitis/oral mucositis/mouth ulcers is as follows:

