6.1.2 Case Report Forms

Data may be entered from the source documents directly into eCRFs in C3D for each patient enrolled in this study. The principal investigator or research nurse will review the eCRFs for completeness and accuracy. Site personnel may also conduct independent audits to ensure completeness and accuracy of data in C3D.

Only the following adverse events will be recorded on the Case Report Form:

- Grade 2 unexpected events that are possibly, probably or definitely related to the study drugs;
- Grade 3 and 4 events that are possibly, probably or definitely related to the study drugs;
- Grade 5 events regardless of attribution;
- Serious Events regardless of attribution.

Patients who meet the standard of care criteria for resection of their disease will undergo a major operative procedure and may receive extensive care in the ICU. The principal investigator or designee will closely monitor and document the clinical care and treatment of each patient as per standard of care at the NIH Clinical Center. As per NIH Clinical Center standards of practice, the Occurrence Reporting System will be used to report any clinical events meeting these reporting criteria.

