80% and 95% confidence intervals to explore whether the present results exceed those from prior studies. In addition, the Kaplan-Meier curves for all patients who received either sunitinib and everolimus as their treatments may be combined into one pooled Kaplan-Meier curve if the two curves for these treatments are sufficiently similar to one another ($p > 0.30$ by a two-tailed log-rank test). This combined curve will then be evaluated relative to the published median of 11 months PFS for each arm to provide a more powerful comparison relative to the historically expected results. In addition, Kaplan-Meier curves limited to the patients who received targeted therapy based solely on mutation status may be constructed for exploratory and descriptive purposes.

Response and overall survival will also be evaluated as secondary endpoints, based on the patients treated with sunitinib or everolimus, using all patients receiving treatment. These results will be descriptive and may consist of fractions of responses as well as Kaplan-Meier curves for survival. The association between genotype and PFS will be explored by evaluating the results within a treatment based on the major genotype categories identified. Safety will be evaluated by tabulating and reporting the distribution of the worst grade of each type of toxicity found, per patient, separately by arm. Should any particular type of toxicity result in 5 or more patients with grade 3-4 toxicity, a comparison of the distributions of toxicity between the two arms may be performed using a Cochran-Armitage test for trend.

Because the patients may not end up being assigned in equal proportions to the two arms, and because the goal is to have 44 evaluable patients who have received each treatment, additional patients beyond the 44 described above may be enrolled on the arm with faster accrual. As such, the study will have an accrual ceiling of 120 patients, with accrual ending when there are 44 evaluable patients on the arm with fewer patients. An amendment may also be needed if a lower proportion of patients than expected receive study drug therapy or if a high portion of treated patients are not evaluable for response. It is anticipated that 20-30 patients per year may enroll onto this trial; thus, accrual may be completed in 4-5 years.

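### Everolimus-only instructions on mouth ulcers and rash can make the by-arm toxicity table in Section 8 not comparable; the rash instruction also conflicts with the CRF recording rule

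*Combined protocol and SAP*

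**What the plan says.** Section 4.1.2 covers everolimus toxicities only. Two of its subsections tell investigators how to report or classify an event.

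- **Oral toxicity, Section 4.1.2.6:** "If your examination reveals mouth ulcers rather than a more general inflammation of the mouth, please classify the adverse event as such". The text adds that investigators in earlier everolimus trials described the oral toxicity as mouth ulcers rather than as mucositis or stomatitis.
- **Rash, Section 4.1.2.2:** "Rash must be reported as an AE". The sentence gives no grade and does not mention the CRF. It stands between a sentence on grade 1 skin toxicity and one on grade 2 or higher.

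Sunitinib has no counterpart to either. Its own supportive-care section, 4.1.1, deals with hypertension.

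The general recording rule is in Section 6.1.2: "Only the following adverse events will be recorded on the Case Report Form". Four classes follow:

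- at grade 2, only those events that are both unexpected and judged at least possibly caused by treatment
- at the next two grades, "Grade 3 and 4 events that are possibly, probably or definitely related to the study drugs"
- fatal events, whatever the cause
- anything serious, again whatever the cause

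The list refers to the study drugs in general and makes no exception by arm. Section 7.2.2 likewise exempts grade 1 events from continuing-review reporting without distinguishing the drugs.

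Section 8 tabulates each patient's worst grade for each type of toxicity, by arm. Once at least five patients have a grade 3 or 4 event of one type, "a comparison of the distributions of toxicity between the two arms may be performed using a Cochran-Armitage test for trend".

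**The concern.** The table and the test work on types of toxicity, so they compare the arms fairly only if an event is recorded, and given the same name, in the same way under both drugs.

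For oral toxicity, one arm is told to divide what it sees over more terms than the other. Each everolimus row then holds fewer patients than it would under a common term, and no single row is as likely to reach the five-patient trigger. The effect would be to understate an everolimus excess, or to leave it untested. Stomatitis is the most common everolimus event that Section 11.2.4 reports (64%), so the split falls on that drug's leading toxicity.

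For rash, the everolimus instruction and the CRF list point in opposite directions. A site that follows Section 4.1.2.2 would collect low-grade rash under everolimus and not under sunitinib, and the table would show a difference that comes from recording alone.

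**Working it through.** The plan states no figure on this point, so there is none to reproduce. The calculations below only give scale.

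**Oral toxicity**

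Inputs:
- 44 patients per arm, 88 in all (Section 8).
- Trigger of five or more patients with grade 3-4. Section 8 does not say whether this is pooled or per arm; pooled is assumed.
- Everolimus grade 3-4 rate: 5% and just under 10%. These are chosen from the band of 1% to under 10% in which Section 11.2.4 lists grade 3/4 stomatitis.
- Sunitinib grade 3-4 rate: not given in the documents. 1% is assumed, with 3% as an alternative.
- Share of everolimus cases coded as mouth ulcers: assumed to be one half.

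Formula: with X_E ~ Binomial(44, p_E) and X_S ~ Binomial(44, p_S), independent, the chance of reaching the trigger is P(X_E + X_S ≥ 5). Splitting replaces p_E by p_E/2 in the shared row.

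| Everolimus | Sunitinib | One term | Shared term after split |
|---|---|---|---|
| 5% | 1% | 12.4% | 1.9% |
| 5% | 3% | 27.6% | 9.6% |
| just under 10% | 1% | 53.7% | 12.4% |
| just under 10% | 3% | 68.6% | 27.6% |

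The separate ulcer row, if filled by everolimus patients only, reaches five with probability 0.5% (p_E = 5%) or 6.7% (just under 10%). With sunitinib at 1%, the chance that either row triggers is therefore at most 1.9% + 0.5% = 2.4%, or 12.4% + 6.7% = 19.1%, against 12.4% and 53.7% with one term.

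**Rash**

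The two rules side by side, for a non-serious rash:

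| Rash | Section 6.1.2, either drug | Section 4.1.2.2, everolimus only |
|---|---|---|
| Grade 1 | not recorded | to be reported (no grade limit) |
| Grade 2, expected | not recorded | to be reported (no grade limit) |
| Grade 3-4, related | recorded | to be reported |

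The rules differ only in the first two rows, and nothing in the protocol ranks them.

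- *If Section 6.1.2 governs:* both arms are recorded alike and no difference arises from recording.
- *If sites follow Section 4.1.2.2:* take the sunitinib rates in Section 1.2.3.3 (13% any grade, 1% grade 3-4) as the true rates in both arms. Expected patients with recorded rash are 44 × 0.13 = 5.7 under everolimus and 44 × 0.01 = 0.4 under sunitinib. That is about 6 against 0-1, with no true difference.

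The rash trigger is the same under either reading, because it counts grade 3-4 events only. With sunitinib at 1%, the chance of reaching it is 0.2%, 3%, 12% and 54% for everolimus grade 3-4 rates of 1%, 3%, 5% and just under 10%. The formal rash test may therefore often not run, but the by-arm table is produced in any case.

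**The case against.** The strongest objection concerns rash. The CRF list is closed and covers both drugs, while Section 4.1.2.2 names neither the CRF nor a grade. Calling a rash an adverse event adds little, since Section 7.1.1 already makes any abnormal sign an adverse event under either drug. Applied evenly, the list gives equal capture. This stands, and it is why the rash point is a conflict to be reconciled and not a demonstrated bias. It does not remove the conflict. Related grade 3-4 rash is already on the list, so the everolimus sentence adds something mainly if it reaches lower grades. Reading it as any grade is a fair inference, but it is not in the text.

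On oral toxicity, it can be said that the instruction only asks for accurate description, that Section 6.4 applies CTCAE v4.0 to the whole study, and that the same team may well record ulcers as ulcers under sunitinib. It is true that the share coded as ulcers is unknown. But a common grading scale does not supply the missing sunitinib instruction, and no other passage neutralises the one given for everolimus.

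Finally, safety is a secondary objective, the test is optional, and the arms are formed by genotype. All of that stands and limits the weight of the point.

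**Conclusion.** The point holds as a minor one, in two parts.

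The oral part holds on the text: the instruction is for one drug only, and Section 8 works by type of toxicity. Its size depends on assumed grade 3-4 rates, an assumed half coded as ulcers and a pooled trigger. The direction does not depend on these values: any split lowers the shared everolimus row.

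The rash part is an unreconciled conflict between Sections 4.1.2.2 and 6.1.2. It biases the low-grade rows only if sites follow the former. Grade 3-4 rash counts and the rash trigger are not affected.

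Two stronger readings are tempting, and the documents support neither.

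- A reader might infer that the table will certainly set all-grade everolimus rash (49% in Section 11.2.4) against grade 3-4 sunitinib rash (1% in Section 1.2.3.3). That applies the CRF list to one drug and not the other. The two rates also come from different study populations.
- A reader might apply the ulcer split to the 64% all-grade stomatitis rate. The CRF list omits non-serious grade 1 and expected grade 2 events under both drugs, so planned CRF data would not yield that row.

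**What to change.** 1. **Section 8:** treat stomatitis, oral mucositis, oral mucosal inflammation and mouth ulcers as one type of toxicity in both arms for the worst-grade table, the five-patient trigger and the trend test. Keep the separate terms as a descriptive breakdown.
2. **Sections 4.1.2.2 and 6.1.2:** state one rash recording rule for both drugs and say which section governs. Either record rash at every grade under both, or remove the everolimus-only sentence. Until that is settled, compare rash between arms at grade 3 or higher only.

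The cost is about two sentences, plus a few CRF lines if low-grade rash is to be recorded under both drugs. The grouped oral term and the grade 3 restriction give less detail in the comparison; the descriptive breakdown keeps the detail for the oral terms. Treatment of patients is not touched.

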4.1.2.3 Management of Hypersensitivity reactions

Hypersensitivity reactions manifested by symptoms including, but not limited to, anaphylaxis, dyspnea, flushing, chest pain or angioedema (e.g. swelling of the airways or tongue, with or without respiratory impairment) have been observed with everolimus.

4.1.2.4 Angioedema with concomitant use of angiotensin-converting enzyme (ACE) inhibitors

Patients taking concomitant ACE inhibitor therapy may be at increased risk for angioedema (e.g. swelling of the airways or tongue, with or without respiratory impairment).

4.1.2.5 Renal Failure Events

Cases of renal failure (including acute renal failure), some with fatal outcome, occurred in patients treated with everolimus. Renal function of patients should be monitored particularly where patients have additional risk factors that may further impair renal function.

Elevations of serum creatinine, usually mild, and proteinuria have been reported in patients taking everolimus. Monitoring of renal function, including measurement of blood urea nitrogen (BUN), urinary protein, or serum creatinine, is recommended prior to the start of everolimus therapy and periodically thereafter.

